### **8.2 Secondary Endpoints**

The secondary endpoint is the VAS score for happiness. We will assess whether there is a change in the VAS happiness score before and after a relaxation session, with a clinically relevant threshold of 0.5 out of 10.

Additionally, physiological parameters measured using the Embrace Plus device are also considered important secondary endpoints.

---

## **9. Design of the Clinical Investigation**

The study design is a crossover randomized controlled trial. In this way, each participant serves as their own control, which helps eliminate individual/genetic effects on the measurements. Since this study involves a heterogeneous patient population with varying diagnoses and comorbidities, this design helps limit variability to obtain statistically significant results with a feasible sample size. It also minimizes the influence of external factors on the study outcomes.

The study protocol was extensively tested among volunteer staff members at Sint-Jan Baptist to identify and resolve potential errors or problems before the official start of the trial, ensuring a relevant and high-quality protocol.

This is also the first clinical study to test the VRelax app in a forensic psychiatric inpatient population, while also incorporating physiological parameters.

---

## **10. Population**

### **10.1 Number of Subjects**

The primary endpoint selected is a change in the VAS relaxation score, where an average improvement of 0.5 out of 10 is considered clinically relevant between pre- and post-session time points.

The standard deviations used (0.83 for standard relaxation and 0.74 for VRelax) were estimated based on the results of a comparable study in an outpatient population, as described in the article by Veling et al. (2021).

The chosen statistical power is 80%, and the type I error rate was set at 0.05.

An expected dropout rate of 30% was included.

Calculations were performed using the GPower software.

The calculated required sample size for detecting a difference in VAS relaxation scores is **54**.

All participants are forensic psychiatric patients admitted to PC Sint-Jan Baptist in Zelzate and expected to remain there for at least 4 more months, ensuring their availability throughout the entire study period.

---

### **10.2 Vulnerable Population (pregnant, children, elderly, immune-compromised or breastfeeding individuals)**

No vulnerable populations will participate in this study.

If a patient is under legal guardianship, consent must be obtained from the legal guardian for participation.

Participation is only possible after a positive recommendation from the medical support team of the patient's unit. The patient's therapy schedule will be temporarily adjusted to allow participation without negative consequences.

---

### **10.3 Inclusion Criteria**

Patients will be included if they are forensic psychiatric patients (aged 18 or older) admitted to PC Sint-Jan Baptist in Zelzate, with an expected stay of at least four more months to ensure full participation. Final inclusion is only possible after approval by the patient's unit medical support team and with the patient's own consent.

---

### **10.4 Exclusion Criteria**

Exclusion criteria include:

Acute psychosis, acute mania, epilepsy, pacemaker, balance disorders, individuals in acute withdrawal from substance or alcohol use, severe cardiac conditions, serious eye disorders, pregnancy, or fear of using VR.

---

### **10.5 Withdrawal and Replacement of Subjects**

#### **Criteria for Withdrawal**

Subjects may discontinue the clinical investigation at any time. A premature discontinuation is defined as a subject not undergoing the end-of-study evaluation.

Subjects can be withdrawn under the following circumstances:

- At their own request
- If the investigator believes continued participation is not in the subject's best interest
- If the subject violates the informed consent terms or disregards investigator instructions
- In the case of significant non-compliance with the study intervention
- If the subject develops VR sickness or an eye condition that makes VR headset use no longer possible
- If treatment is discontinued and the patient is discharged from the hospital

In all cases, the reason for withdrawal must be thoroughly documented in the (e)CRF and the subject's medical record.

A subject will be considered lost to follow-up if they do not return for scheduled visits and cannot be contacted by study staff.

#### **Follow-up actions include:**

- Attempt to contact and reschedule the visit
- At least 3 phone call attempts and, if needed, a certified letter to the subject's last known address
- If still unreachable, the subject is considered a dropout due to loss to follow-up

#### **Replacement Policy**

Dropouts will be registered during the study, including the reason for discontinuation. If the number of dropouts is too high and threatens the quality of the research, additional participants will be recruited.

---

#### **10.6 Restrictions and Prohibitions for the Subjects**

Patients are not required to follow any additional restrictions for this study. The only request is to avoid intense physical activity immediately before the sessions in order to prevent disruption of physiological measurements.

---

#### **10.7 Possible Advantages and Risks for the Subjects**

Patients at PC Sint-Jan Baptist are under no obligation to participate in this study. Participation or refusal to participate will have no impact on their ongoing treatment.

Participation may result in a reduction in stress levels, but it is also possible that no benefits or results will be observed. However, the findings of this study may lead to the development of new and more effective methods for treating stress using emerging technologies such as Virtual Reality.

As Virtual Reality is a widely used and commercially available technology, and the VRelax software has already obtained a European conformity certificate, potential health risks are considered minimal. The likelihood of harm from participation is extremely low. If VR sickness occurs during sessions, symptoms such as nausea or dizziness are typically mild and short-lived.

It is possible that unknown risks or discomforts may arise during the study. Therefore, it is crucial to report any new health complaints to the researcher as soon as possible, regardless of whether the participant believes it is related to the study.

Participants have the right to ask questions at any time regarding the known or potential risks of the study. If new information becomes available during the study that may affect a participant's willingness to continue, they will be informed promptly. Should any harm arise from participation, appropriate treatment will be provided.

---

## **11. Identification and Description of the Investigational Device**

### **11.1 Medical Device Description**

This study uses PICO VR headsets and Embrace Plus monitoring devices. Both devices are market-compliant and are being used for their intended purpose in this study.

The VRelax software is a VR relaxation program that utilizes 360° videos, also used in accordance with its design. This software has received EU conformity certification.

### **11.2 Manufacturer**

- PICOXR.com
- VRelax.com
- Empatica.com

---

### **11.3 Intended Use**

VR headsets are widely used both commercially and professionally for a variety of purposes, including gaming, leisure, therapy, and training/education.

---

### **11.4 Instructions for Use**

Refer to the user manual.

---

### **11.5 Delivery and Return of the Medical Device**

The VR headsets and Embrace Plus devices have already been purchased and tested, as has the VRelax software. The license for VRelax and the accompanying GRIP app will be renewed annually. Two Apple iPad Pros were also purchased for use with the GRIP viewer app for VRelax.

---

### **11.6 Storage of the Medical Device**

All equipment is stored in the hospital's VR room, where the study sessions will also take place. This room is accessible only to authorized personnel.

---

### **11.7 Traceability and Accountability of the Medical Device**

The devices are registered in our list of medical equipment, maintained through the hospital pharmacy.

---

### **11.8 Known Reactions/Side Effects of the Medical Device**

Known side effects of VR include VR sickness, which may present as nausea, dizziness, or dry eyes.

---

## **12. Identification and Description of the Comparative Device**

(Not applicable or not specified)

---

## **13. Methodology**

### **13.1 Study-Specific Procedures**

The study consists of two blocks of 10 sessions: one block with VR and one without. Each participant thus serves as their own control.

The control sessions take place in the VR room, seated, with a total duration of 30 minutes (including 20 minutes of relaxation of their choice, e.g., reading, listening to music, watching a short film, body scan, etc.). The selected relaxation method is recorded for each session.

The VR sessions also take place in the VR room, seated, with a duration of 30 minutes (including 20 minutes of VRRelax with one or more 360° videos of the participant's choice). Guided meditation sessions are excluded, as they require the eyes to be closed. The selected videos are recorded per session.

Before and after each session, stress is assessed using VAS scores for stress/tension and happiness. At the beginning and end of each 10-session block, general stress levels are measured using the Perceived Stress Scale (PSS). After the final session of each block, a structured qualitative interview is conducted regarding the user experience. All groups receive the same pre- and post-intervention assessments.

During each relaxation session, physiological parameters are also measured using the Embrace Plus device ([www.Empatica.com](http://www.Empatica.com)), including heart rate, heart rate variability (HRV), respiratory rate, skin conductance, and skin temperature.

---

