### **7.2 Secondary Objectives**

This study also serves to provide a scientifically grounded basis for deciding whether to implement VR in clinical practice. Therefore, we will evaluate applicability, usability, and implementation potential of the technology. Is investment in this relatively expensive technology justified?

Additionally, this study will help identify possible barriers and challenges associated with VR usage. It also serves as a starting point for the implementation of other e-health technologies in the future, with the experience and expertise gained through this study becoming a valuable asset.

---

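### The user-experience interview has no time point at early stopping, so interview-based usability findings on VR would come from patients who finished the VR block and may look too favourable

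*Combined protocol and SAP*

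**What the plan says.** Section 7.2 sets the objective. To support a decision on whether to implement VR, "we will evaluate applicability, usability, and implementation potential of the technology", and "this study will help identify possible barriers and challenges associated with VR usage". The same section asks whether the expense of the technology is justified. The Synopsis also lists feasibility and user-friendliness among the secondary objectives.

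Section 13.1 describes the one instrument dedicated to user experience: "After the final session of each block, a structured qualitative interview is conducted regarding the user experience". There are two blocks of 10 sessions, one with VR and one without.

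The plan expects some participants to stop. Section 10.1 states: "An expected dropout rate of 30% was included". Section 10.5 lists among the withdrawal circumstances: "If the subject develops VR sickness or an eye condition that makes VR headset use no longer possible".

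For those who stop, section 10.5 says: "In all cases, the reason for withdrawal must be thoroughly documented in the (e)CRF and the subject's medical record". Its Replacement Policy adds: "Dropouts will be registered during the study, including the reason for discontinuation". Section 24.2 repeats the requirement for the eCRF, and section 14.3.1 has adverse events recorded from first device use onwards.

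Section 16.2 covers the VAS scores, the physiological parameters and the PSS. It says nothing about interview data or withdrawal reasons.

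**The concern.** A participant who stops the VR block partway never reaches its final session, which is the only trigger for the interview. These participants are likely to know most about what makes VR hard to use in this setting. The plan itself anticipates such reasons: VR sickness is a known side effect (section 11.8), and the fourth hypothesis allows for habituation or boredom. Under section 10.4, people afraid of using VR are also excluded at entry, so the interviewed group is already selected towards acceptance.

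What is at stake is the section 7.2 conclusion on usability and barriers, which is meant to inform an investment decision. If interviews reach only those who completed 10 VR sessions, that part of the evidence probably leans towards VR. An interview missed at the time of stopping cannot be reliably reconstructed later.

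**Working it through.** **1. Inputs.** Planned sample 54 and expected dropout 30% (sections 10.1 and 16.1); interview after the last session of each block (13.1). The documents do not say when dropouts are expected to occur.

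**2. The plan's own figure.** 54 can be reproduced as follows. Take a paired t-test, difference 0.5, SDs 0.83 and 0.74, two-sided alpha 0.05 and power 80%. Two-sidedness and a within-patient correlation of 0 are assumptions.
- SD of the difference = √(0.83² + 0.74²) = 1.112
- Required n = 41
- 41 × 1.3 = 53.3, rounded up to 54

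Other routes come close, and the documents do not say which was used. The present point needs only the stated 54 and 30%.

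**3. Expected dropouts.** 54 × 0.30 = 16.2, so about 16 stop early. 54 × 0.70 = 37.8, so about 38 complete both blocks.

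**4. How many lack a VR interview.** Let s be the share of dropouts who leave before finishing the VR block. The number without a VR interview is 54 × 0.30 × s.

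| s (assumed) | Without a VR interview | Share of 54 |
|---|---|---|
| 0% | 0 | 0% |
| 25% | 4.05, about 4 | 7.5% |
| 50% | 8.1, about 8 | 15% |
| 75% | 12.15, about 12 | 22.5% |
| 100% | 16.2, about 16 | 30% |

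A participant who completes VR first and leaves during the standard block still gives a VR interview, so s can be well below 100%. A participant allocated to standard relaxation first who leaves before starting VR is counted in the table but has no VR experience to report. The number with unreported VR experience is therefore at most the number shown.

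**5. What is collected from someone who stops during the VR block.**

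| Source | Collected? | Bearing on 7.2 |
|---|---|---|
| Reason for withdrawal (10.5, 24.2) | Yes | Main reason only; withdrawal at the participant's own request is a listed circumstance and can be recorded with no usability content |
| Adverse events (14.3.1) | Yes | Nausea or dizziness, but not dislike, boredom or trouble with the headset or videos |
| VAS, video choices, physiology (13.1) | Yes, for sessions attended | Response and preference, not user experience |
| Structured interview (13.1) | No | The dedicated instrument |

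The gap is therefore specific: the structured account is missing, and section 16.2 does not say how the other sources will be read alongside the interviews.

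**The case against.** The strongest reply is that early stoppers are not lost to the barriers question. A reader might infer from 13.1 that they are never asked why they stopped. The documents contradict this: the reason must be recorded in every case (10.5, its Replacement Policy and 24.2). A reader might also infer that the objective is answered by completers alone. That is too broad. Adverse events, including VR sickness, are recorded in non-completers; session data exist for the sessions they attended; and some dropouts will already have given a VR interview.

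It can also be said that section 7.2 does not name the interview as its only source, that user experience is not an endpoint in 8.1 or 8.2, and that a participant may stop for reasons unrelated to VR, such as discharge. The direction of any bias is plausible rather than established. The interview is qualitative and the documents give no rates of reported barriers, so a bias in percentage points could be obtained only from assumed inputs. None is offered here.

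All of this stands, and it limits the point to a minor one. It does not remove it. A recorded reason or an adverse event entry is not comparable with a structured interview, and 16.2 sets out no use of either for the usability and barriers objective.

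**Conclusion.** The point holds in a limited form. Followed as written, section 13.1 yields no structured interview from participants who stop during the VR block, and section 16.2 does not bring their recorded reasons and adverse events into the section 7.2 objective. Interview-based findings on VR would come from VR-block completers and may look too favourable.

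The size is 0 to about 16 of 54 participants without a VR interview, and about 8 if half of the dropouts stop before completing VR. This assumes that the planned 30% dropout occurs; its timing is unknown. About 16 is an upper limit, not an expected count.

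Severity is minor. The VAS and physiological endpoints and their analyses are not affected.

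**What to change.** In section 13.1, replace the interview sentence with: *The structured interview is held after the final session of each block, or when the participant stops that block early, whichever comes first, if the participant agrees.*

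In section 16.2, add: *Usability and barriers are reported for all participants who started the VR block, giving the number interviewed, the number who stopped VR early, and their recorded reasons and VR-related adverse events beside the interview results.*

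Cost: two sentences and a small number of added interviews, using the same form and staff. Each dropout interrupts at most one block, so at 30% dropout there would be at most about 16 extra interviews across both blocks. Some participants who stop will decline, and some will already have been discharged, so the gap will narrow rather than close. Reporting how many were not interviewed shows the reader what remains.

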### **13.2 Flowchart**

1. Information sessions per ward and registration of candidate participants
2. Approval for participation by the patient's medical team
3. Final inclusion of the participant
4. Start of the experiment
5. End of the experiment
6. Data processing

### **13.3 Start of the Clinical Investigation**

During a group session on each ward, the study will be explained, and patients will be asked whether they are interested in participating. After this session, individual caregivers will have one week to ask the patient whether or not they wish to participate. Patients who express interest will be discussed during the ward's multidisciplinary team meeting two weeks after the information session. Their participation will then be formally approved or declined.

Once approved, the ward psychologist will provide the investigator with the list of participants. The therapy schedules of the patients will then be adjusted to enable participation in the planned relaxation sessions.

---

### **13.4 End of the Clinical Investigation**

The expected duration of participation for each patient is a maximum of 4 months. The entire study will have a maximum duration of 3 years.

---

### **13.5 Randomisation**

As soon as all participants are confirmed, randomisation will be carried out using SAS software to assign them to one of the two groups.

---

### **13.6 Prior and Concomitant Medication/Treatments**

There are no restrictions.

## **14. Safety reporting**

### **14.1. Definitions**

#### **Adverse Event (AE)**

Any untoward medical occurrence, unintended disease or injury or any untoward clinical signs (including an abnormal laboratory finding) in subjects, users or other persons, in context of a clinical investigation, whether or not related to the investigational medical device. (MDR Art 2(57))

Note:

- a. This definition includes events that are anticipated as well as unanticipated events
- b. This definition includes events occurring in the context of a clinical investigation related to the investigational device, the comparator or the procedures involved.

#### **Serious Adverse Event (SAE)**

Any adverse event that led to any of the following:

- a) death,
- b) serious deterioration in the health of the subject, that resulted in any of the following:
  - i. life-threatening illness or injury,
  - ii. permanent impairment of a body structure or a body function,
  - iii. hospitalisation or prolongation of patient hospitalisation,
  - iv. medical or surgical intervention to prevent life-threatening illness or injury or permanent impairment to a body structure or a body function,
  - v. chronic disease,

c) foetal distress, foetal death or a congenital physical or mental impairment or birth defect  
(MDR Article 2(58))

### **Device deficiency**

Any inadequacy in the identity, quality, durability, reliability, safety or performance of an investigational device, including malfunction, use errors or inadequacy in information supplied by the manufacturer.

### **Adverse Device Effect (ADE)**

Adverse event related to the use of an investigational medical device.

NOTE 1- This includes any adverse event resulting from insufficiencies or inadequacies in the instructions for use, the deployment, the implantation, the installation, the operation, or any malfunction of the investigational medical device.

NOTE 2- This includes any event that is a result of a use error or intentional abnormal use of the investigational medical device.

### **Serious Adverse Device Effect (SADE)**

Adverse device effect that has resulted in any of the consequences characteristic of a serious adverse event.

### **Unanticipated Serious Adverse Device Effect (USADE)**

Serious adverse device effect which by its nature, incidence, severity or outcome has not been identified in the current risk assessment. Procedures associated with the use of a device should be addressed in the risk assessment, which makes it possible to determine whether the procedure related SAEs are Unanticipated Serious Adverse Device Effect or not. SAEs related to procedures imposed by the clinical investigation plan but not with the use of the device should not be considered Serious Adverse Device Effects.

NOTE: Anticipated SADE (ASADE): an effect which by its nature, incidence, severity or outcome has been previously identified in the risk assessment.

## **14.2. Causality assessment**

The relationship between the use of the medical device (including the medical – surgical procedure) and the occurrence of each adverse event shall be assessed and categorized. During causality assessment activity, clinical judgment shall be used and the relevant documents, such as the Investigator's Brochure and the Clinical Protocol shall be consulted, as all the foreseeable serious adverse events and the potential risks are listed and assessed there. The presence of confounding factors, such as concomitant medication/treatment, the natural history of the underlying disease, other concurrent illness or risk factors shall also be considered.

For the purpose of harmonizing reports, each SAE will be classified according to four different levels of causality. The investigators and the sponsor will use the following definitions to assess the relationship of the serious adverse event to the investigational medical device, the comparator or the investigation procedures.

**1) Not related:** relationship to the device or procedures can be excluded when:

- the event has no temporal relationship with the use of the investigational device, or the procedures related to application of the investigational device;
- the serious adverse event does not follow a known response pattern to the medical device (if the response pattern is previously known) and is biologically implausible;
- the discontinuation of medical device application or the reduction of the level of activation/exposure - when clinically feasible - and reintroduction of its use (or increase of the level of activation/exposure), do not impact on the serious adverse event;
- the event involves a body-site or an organ that cannot be affected by the device or procedure;
- the serious adverse event can be attributed to another cause (e.g. an underlying or concurrent illness/ clinical condition, an effect of another device, drug, treatment or other risk factors);
- the event does not depend on a false result given by the investigational device used for diagnosis, when applicable;

In order to establish the non-relatedness, not all the criteria listed above might be met at the same time, depending on the type of device/procedures and the serious adverse event.

**2) Possible** the relationship with the use of the investigational device or comparator, or the relationship with procedures, is weak but cannot be ruled out completely. Alternative causes are also possible (e.g. an underlying or concurrent illness/ clinical condition or/and an effect of another device, drug or treatment). Cases where relatedness cannot be assessed or no information has been obtained should also be classified as possible.

**3) Probable** the relationship with the use of the investigational device or comparator, or the relationship with procedures, seems relevant and/or the event cannot reasonably explained by another cause.

**4) Causal relationship:** the serious event is associated with the investigational device, comparator or with procedures beyond reasonable doubt when:

- the event is a known side effect of the product category the device belongs to or of similar devices and procedures;
- the event has a temporal relationship with investigational device use/application or procedures;
- the event involves a body-site or organ that
  - o the investigational device or procedures are applied to;
  - o the investigational device or procedures have an effect on;
- the serious event follows a known response pattern to the medical device (if the response pattern is previously known);
- the discontinuation of medical device application (or reduction of the level of activation/exposure) and reintroduction of its use (or increase of the level of activation/exposure), impact on the serious adverse event (when clinically feasible); other possible causes (e.g. an underlying or concurrent illness/ clinical condition or/and an effect of another device, drug or treatment) have been adequately ruled out;
- harm to the subject is due to error in use;
- the event depends on a false result given by the investigational device used for diagnosis, when applicable;

In order to establish the relatedness, not all the criteria listed above might be met at the same time, depending on the type of device/procedures and the serious adverse event.

The sponsor and the investigators will distinguish between the serious adverse events related to the investigational device and those related to the procedures (any procedure specific to the clinical investigation). An adverse event can be related both to procedures and the investigational device. Complications caused by concomitant treatments not imposed by the clinical investigation plan are considered not related. Similarly, several routine diagnostic or patient management procedures are applied to patients regardless of the clinical investigation plan. If routine procedures are not imposed by the clinical investigation plan, complications caused by them are also considered not related..

In some particular cases the event may be not adequately assessed because information is insufficient or contradictory and/or the data cannot be verified or supplemented. The sponsor and the Investigators will make the maximum effort to define and categorize the event and avoid these situations. Where an investigator assessment is not available and/or the sponsor remains uncertain about classifying the serious event, the sponsor should not exclude the relatedness and classify the event as "possible" and the reporting should not be delayed.

Particular attention shall be given to the causality evaluation of unanticipated serious adverse (device) events. The occurrence of unanticipated events related could suggest that the clinical investigation places subjects at increased risk of harm than was to be expected beforehand.

